- If a patient experiences a Grade 3 or 4 non-drug-related renal function impairment or hepatic function impairment, MLN9708, can be held until recovery to Grade 1 or baseline (up to a maximum of 14 days). Upon recovery of the toxicity to a level allowing continuation of therapy, a dose reduction is not necessary.

Duration of therapy

MLN9708 will be continued until any one of the following criteria is met:

- Patient finishes four doses of MLN9708.
- Patient develops grade III-IV acute GVHD.
- Patient develops severe chronic GVHD.
- Patient develops any grade 3-4 toxicity related to MLN9708 use.

Data Safety Monitoring Plan

The Medical College of Wisconsin (MCW) Cancer Center (CC) Data Safety Monitoring Committee (DSMC) is responsible for monitoring data quality and subject safety for all cancer center investigator initiated clinical trials. A six to eight member Data and Safety Monitoring Committee will complete a review of protocol-specific data safety monitoring reports, to provide recommendations on trial continuation, suspension or termination.

A summary of the MCW CC DSMC activities are as follows:

- Review the clinical trial for data integrity and safety
- Review all unexpected grade 3, and all grade 4, and 5 adverse events, as well as any others requiring expedited reporting as defined in this protocol. (Grades 4 & 5 events must be reported to the DSMC within 5 calendar days of study staff's knowledge.)
- Review all DSMC reports
- Submit a summary of any recommendations related to study conduct
- Terminate the study if deemed unsafe for patients

A copy of the MCW CC Data and Safety Monitoring Plan and membership roster will be maintained in the study research file and updated as membership changes. The committee will

review reports from the study PI twice annually (or more frequently if needed) and provide recommendations on trial continuation, suspension or termination as necessary.

Any available DSMC letters will be submitted to the IRB of record as required.

6. Measurement of Effect:

Follow up schedule:

The schedule for follow up on the study is shown in the table below.

Study Visit	Approximate target Day Post-Transplant
1	60 days
2	67 days
3	74 days
4	81 days
5	90-100 days
6	180 days
7	365 days
8	2 years

Patients will be followed for survival, relapse and cause of death for 5 years post transplantation.

Phase I patients will be seen weekly for toxicity assessment during the DLT period.

GVHD Assessment:

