concluding the new treatment is promising, will be 0.80 (statistical power) when the true but unknown rate of developing chronic GVHD is 30% or 0.04 (type I error) when the true rate is 55% in related donor transplantation (Cohort A [matched sibling donor transplantation] with a sample size of 25). Similarly, the probability of concluding the new treatment is promising, will be 0.81 (statistical power) when the true but unknown rate of developing chronic GVHD is 40% or 0.05 (type I error) when the true rate is 65% in unrelated transplantation (Cohort B [unrelated donor transplantation] with a sample size of 26). The efficacy endpoint is chronic GVHD-free at 1 year and there will be no interim analysis on efficacy for this multi-center study. In the final analysis in Cohort A, if 10 or more of 25 patients have chronic GVHD, we will conclude the new treatment is ineffective in Cohort A; for Cohort B, if 13 or more of 26 patients have chronic GVHD, we will conclude the new treatment is ineffective in Cohort B.

Demographic and baseline laboratory results will be summarized using descriptive statistics, including means with standard deviations, or medians with ranges, histograms and box-plot. The chronic GVHD rate at 1-year and its 95% CI will be calculated by cumulative incidence method, while accounting for competing events. Progression-free survival and overall survival will be estimated using the Kaplan-Meier method.

Cumulative incidence of acute and chronic GVHD, disease relapse and non-relapse mortality will be calculated by accounting for competing events. Competing events for acute GVHD disease are relapse or death without acute GVHD, while those for chronic GVHD are relapse or death without chronic GVHD. Disease relapse and non-relapse mortality are competing events for each other. Toxicity will be reported by type, frequency and severity. Worst toxicity grades per patient will be tabulated for selected adverse events and laboratory measurements. Patients replaced on the protocol (as specified in the Dose Modification Section) will remain evaluable for safety and toxicity assessment.

Safety/Stopping Rules:

For the phase II portion of the study we propose to accrue 51 patients over 24–30 months, which will enroll about 12 patients every 6 month time period. We plan to

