monitor and evaluate short term adverse events at each additional 12 patients who have been enrolled in the study. The expected 100 day post-transplant immunologic graft rejection (defined as less than 5% donor myeloid cells) rate is approximately 2.5% (in absence of relapsed disease) and the enrollment will be put on hold if more than 5% graft rejection rate is seen. For the development of grade 3-4 adverse events deemed to be related to MLN9708, the true rate is 5% and enrollment will be on hold if more than 10% adverse events are observed. The stopping boundaries for graft rejection and development of grade 3-4 adverse events are shown in Table below. In the case of a safety event suspending study, a prompt cumulative examination of all data and circumstances of these events will be conducted by the Medical College of Wisconsin DSMC to determine whether study should be resumed, whether the protocol will be revised or whether the study will be discontinued permanently.

Table. Stopping boundary for adverse events.

Number of patients enrolled	Stopping boundary for immunologic graft-rejection	Stopping boundary for developing grade 3-4 adverse events related to MLN9708
12	≥ 3	≥ 3
24	≥ 3	≥ 4
36	≥ 4	≥ 6
48	≥ 4	≥ 6
51	≥ 5	≥ 7

Accrual Estimate: 6-12 patients will be enrolled in the phase I part of the protocol. In the phase II portion a total of 52 patients (25 sibling and 27 unrelated donor transplantation) will be enrolled, with 1-3 per month. Total estimated accrual = 58 patients.

Accrual Period : Approximately 24-30 months

Follow-Up Period : Two years to evaluate incidence of acute and chronic GVHD and relapse pattern, and five years for survival outcomes.

10. Adverse Event Reporting Requirements

11. Definitions

The following are definitions of adverse events as defined by 21CFR312.32.

Types of Adverse Events

Adverse Event (AE) means any untoward medical occurrence associated with the use of a drug in humans, whether or not consider drug related. An AE can therefore be any unfavorable and unintended sign (including an abnormal laboratory finding), symptom, or disease temporally associated with the use of a medicinal (investigational) product whether or not it is related to the medicinal product. This includes any newly occurring event, or a previous condition that has increased in severity or frequency since the administration of study drug.

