All unexpected grade 3, and all grade 4, and 5 adverse events, as well as any others requiring expedited reporting as defined in this protocol, will be reported to the MCW Cancer Center DSMC. (Grades 4 & 5 events must be reported to the DSMC within 5 calendar days of study staff's knowledge). If the Grade 3-5 event is determined to be an unanticipated problem, the event will be forwarded to the MCW IRB for review as required by their policy. Unexpected adverse events, regardless of severity, will be reported to the MCW Cancer Center DSMC and reviewed on a quarterly basis.

Expected Adverse Events

Expected adverse events that are being captured on the study toxicity form will be reported at the time of the form's scheduled due date.

All MCW Cancer Center DSMC reports and recommendations will be submitted to the IRB for their review.

Procedures for Reporting AESIs

AEs may be spontaneously reported by the patient and/or in response to an open question from study personnel or revealed by observation, physical examination, or other diagnostic procedures. Any clinically relevant deterioration in laboratory assessments or other clinical finding is considered an AE. When possible, signs and symptoms indicating a common underlying pathology should be noted as one comprehensive event. For non-serious AEs (including AESIs), the investigator must determine both the intensity of the event and the relationship of the event to study drug administration.

AESIs must be reported to Millennium on a quarterly basis.

Procedures for Reporting Drug Exposure during Pregnancy and Birth Events

If a woman becomes pregnant or suspects that she is pregnant while participating in this study, she must inform the investigator immediately and permanently discontinue study drug. The sponsor-investigator must immediately fax a completed Pregnancy Form to the Millennium Department of Pharmacovigilance or designee (see Section Reporting of Adverse Events). The pregnancy must be followed for the final pregnancy outcome.

If a female partner of a male patient becomes pregnant during the male patient's participation in this study, the sponsor-investigator must also immediately fax a completed Pregnancy Form to the Millennium Department of Pharmacovigilance or designee (see Section Reporting of Adverse Events). Every effort should be made to follow the pregnancy for the final pregnancy outcome.

Suggested Pregnancy Reporting Form:

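### The phase II safety text and its boundary table give different enrolment-hold rules for graft rejection and related grade 3-4 events at all five looks

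*Combined protocol and SAP*

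**What the plan says.** The rule is in Section 9 under Safety/Stopping Rules. Rejection by 100 days is expected in about 2.5% of patients, leaving relapsed disease aside. The hold trigger for this event reads: "the enrollment will be put on hold if more than 5% graft rejection rate is seen". For grade 3-4 events related to MLN9708, a true rate of 5% is assumed, and the trigger reads: "enrollment will be on hold if more than 10% adverse events are observed". The text then adds: "The stopping boundaries for graft rejection and development of grade 3-4 adverse events are shown in Table below".

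The table has rows at 12, 24, 36, 48 and 51 enrolled. Its boundaries are at least 3, 3, 4, 4, 5 for rejection and at least 3, 4, 6, 6, 7 for related grade 3-4 events. Section 9 gives no derivation, test level or probability of holding, and does not say whether the sentence or the table takes precedence. Reaching a boundary suspends enrolment and leads to a DSMC review of the cumulative data.

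**The concern.** Both triggers are worded as rates found in the data, so each converts directly into a count at each look. Those counts differ from the table in all ten cells, and the table is always the more permissive. Someone reading the sentence would suspend enrolment after 2 rejections in the first 12 patients (16.7%); someone reading the table would continue.

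Safety is a primary objective of both phases, and this is the only quantitative rule for suspending phase II. Whoever applies it has two answers. A reader of the text would also believe that rates above 5% and 10% lead to a hold, which the table does not deliver.

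**Working it through.** **Inputs (Section 9).** Looks at n = 12, 24, 36, 48, 51. Text triggers c = 5% (rejection) and 10% (related grade 3-4). Expected rates 2.5% and 5%. Table boundaries as listed above.

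**Step 1. Can the table be reproduced from the text?** The smallest count whose observed rate exceeds c is floor(c × n) + 1. For rejection, c × n = 0.6, 1.2, 1.8, 2.4, 2.55. For toxicity, c × n = 1.2, 2.4, 3.6, 4.8, 5.1. The highest rate the table lets pass is (boundary − 1)/n.

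| n | Rejection: text | Rejection: table | Highest rate passing | Toxicity: text | Toxicity: table | Highest rate passing |
|---|---|---|---|---|---|---|
| 12 | 1 | 3 | 2/12 = 16.7% | 2 | 3 | 2/12 = 16.7% |
| 24 | 2 | 3 | 2/24 = 8.3% | 3 | 4 | 3/24 = 12.5% |
| 36 | 2 | 4 | 3/36 = 8.3% | 4 | 6 | 5/36 = 13.9% |
| 48 | 3 | 4 | 3/48 = 6.3% | 5 | 6 | 5/48 = 10.4% |
| 51 | 3 | 5 | 4/51 = 7.8% | 6 | 7 | 6/51 = 11.8% |

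The table is not reproduced in any cell. Every passing rate exceeds its stated trigger.

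**Step 2. Is the table a test against the expected rate?** The exact single-look tail P(X ≥ boundary) is:

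- rejection at 2.5%: 0.0029, 0.0214, 0.0122, 0.0318, 0.0088
- toxicity at 5%: 0.0196, 0.0298, 0.0083, 0.0317, 0.0131

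Taking the smallest count with tail at or below a common level reproduces both columns, but only for a level of about 0.0318 to 0.0323. This is an inference from ten counts; the protocol states no level.

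**Step 3. Probability of ever holding.** Start with all probability at zero events. At each look, convolve with the binomial for the new patients (12, 12, 12, 12, 3), add the mass at or above the boundary to the hold probability, and remove it. For example, the text rule for rejection at its first look gives 1 − 0.975^12 = 0.262.

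| Event | True rate | Table | Literal text | Text, no look at 12 |
|---|---|---|---|---|
| Rejection | 2.5% | 4.2% | 36.6% | 24.9% |
| Rejection | 5% | 24.5% | 68.3% | 60.0% |
| Toxicity | 5% | 5.8% | 21.5% | 17.1% |
| Toxicity | 10% | 40.7% | 66.5% | 63.3% |

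At a true 10% rejection rate the table holds with probability 74.2%; at a true 20% toxicity rate, 95.0%.

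**Step 4. How often would the two rules disagree?** This is the probability that, at some look before any table hold, the count reaches the text trigger but not the table boundary.

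| Event | True rate | All five looks | No look at 12 |
|---|---|---|---|
| Rejection | 2.5% | 36.0% | 22.5% |
| Rejection | 5% | 64.4% | 47.0% |
| Toxicity | 5% | 18.5% | 13.7% |
| Toxicity | 10% | 48.0% | 38.8% |

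**Step 5. Last row.** The safety text says "we propose to accrue 51 patients", while the Accrual Estimate says "In the phase II portion a total of 52 patients (25 sibling and 27 unrelated donor transplantation) will be enrolled". Four rejections hold at 48 but not at 51. A boundary of 4 at 51 would add only 0.6 points to the hold probability at 2.5% and 2.8 points at 5%.

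**The case against.** The strongest reply is that there is one rule, the table. The sentence after the two triggers points to it, and only the table gives counts. Read literally, the text would suspend enrolment after a single rejection in 12 patients, which has a 26% chance at the expected rate. On this view 5% and 10% are unacceptable true rates, loosely worded. That is plausible, and Step 2 is consistent with it. But the protocol states it nowhere, and on that reading the wording of both triggers is wrong.

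It is also fair that no finite boundary can enforce a true rate, and that the plan sets no target hold probability. The 24.5% and 40.7% therefore describe what the table does and do not by themselves show that its boundaries are wrong.

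Four further points stand in part:

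- The disagreement is largest when the 12-patient look is included. Without it the figures fall but remain substantial.
- A hold at 51 has almost no enrolment left to suspend, so four looks matter in practice.
- The ambiguity falls first on whoever applies the hold, since the DSMC reviews after a suspension.
- Other safeguards exist. The DSMC meets on the trial twice a year and may terminate it. Section 5 adds: "Grades 4 & 5 events must be reported to the DSMC within 5 calendar days".

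These limit the harm. None of them settles which trigger suspends enrolment.

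**Conclusion.** The concern holds. Text and table conflict in all ten cells, shown by division on printed numbers, and nothing elsewhere in the protocol resolves it. The two rules differ by 32.4 points for rejection and 15.7 points for toxicity in the chance of a hold at the expected rates (36.6 − 4.2 and 21.5 − 5.8). At the trigger rates they differ by 43.8 and 25.8 points (68.3 − 24.5 and 66.5 − 40.7).

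The probabilities assume independent patients, a common event rate, and all events known at each look. The conflict itself needs none of these assumptions. The efficacy analysis is unaffected, and a hold means review and not automatic termination. Because this is a safety threshold, it should be corrected before it is relied on.

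Two lesser points go with it. The last row does not match the planned 52 patients or sit well with the row at 48. The text also does not say whether a related grade 5 event counts toward a boundary defined for grade 3-4. Section 11 (Unexpected Adverse Events) sends "All unexpected grade 3, and all grade 4, and 5 adverse events" to the DSMC, so such an event would be seen, but its place in the count is unstated.

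**What to change.** Reconcile the sentences and the table in Safety/Stopping Rules, and state which governs.

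- If the table governs: say that enrolment is held when a table boundary is reached, stop describing 5% and 10% as observed-rate triggers, and state the per-look test level and reference rates used.
- If the text governs: recalculate the table to match it (Step 1 gives the counts) and acknowledge the higher chance of a false hold.

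In either case, print the probability of ever holding at the expected rates and at the rates regarded as unacceptable. Align the last row with the planned phase II size and with the row at 48, and state whether related grade 5 events count.

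The cost is amended wording plus a short operating-characteristics table, or a recalculated boundary table. No new patients or data are required.

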One death was reported for a patient with RSV pneumonia; the event was deemed by the investigator to be related to treatment with MLN9708.

Clinical Trial Experience Using the Intravenous Formulation of MLN9708

See the IB for descriptions of the 2 ongoing studies investigating IV MLN9708 in advanced solid tumors and advanced lymphoma (Studies C16001 and C16002, respectively).

Study Rationale:

Proteasome inhibition eliminates alloreactive T cells, interferes with APC function and reduces inflammatory cytokine production either by eliminating the cytokine-secreting cell or by inhibiting its production through the downmodulation of NF- κ B-dependent transcription, supporting the role of proteasome inhibitors as GVHD prophylactic agents. Based on the previously discussed preclinical and limited clinical data, we now propose a phase I/II study of chronic GVHD prophylaxis with oral proteasome inhibitor MLN9708 in patients undergoing matched related or unrelated donor allogeneic transplantation. Phase I will be conducted as a single site study and Phase II as a multi-site study. The additional site, the University of West Virginia, will be added when the Phase II portion of the study is opened. Building on our prior experience showing reduced rates of acute GVHD with an atorvastatin-containing acute GVHD prophylaxis, the *preferred acute GVHD prophylactic regimen* on the current study will be atorvastatin, mini-dose methotrexate and tacrolimus; however the acute GVHD prophylaxis used will remain at the discretion of the treating physician since rate of acute GVHD is not the primary outcome of the current protocol. Furthermore flexibility in type of acute GVHD prophylaxis permitted, will support robust accrual on the current protocol.

Potential Risks and Benefits:

Please refer to the current MLN9708 Investigator's Brochure (IB). MLN9708 is a modified dipeptide boronic acid proteasome inhibitor similar to VELCADE, which has a known safety profile [VELCADE PI]. The most frequent AEs reported to date in the ongoing MLN9708 phase 1 studies were anticipated based on preclinical data and previous experience with VELCADE, and are noted in the IB, the Safety Management Attachment, and the informed consent documents. However, it is possible that MLN9708 will have toxicities that were not previously observed in or predicted from such sources. Patients will be monitored closely for anticipated toxicities.

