Unexpected also refers to adverse events or suspected adverse reactions that are mentioned in the investigator brochure as occurring with a class of drugs or as anticipated from the pharmacological properties of the drug, but are not specifically mentioned as occurring with the particular drug under investigation.

Adverse Event of Special Interest Definition: Adverse Events of Special Interest (AESIs) are a subset of AEs that are to be reported to Millennium on a quarterly basis by the sponsor-investigator. Millennium will provide the current list of AESIs and updates to the list will be distributed to the sponsor-investigator as appropriate.

Adverse Event Grading

Grade	Description
0	No AE (or within normal limits).
1	Mild ; asymptomatic or mild symptoms; clinical or diagnostic observations only; intervention not indicated.
2	Moderate ; minimal, local or noninvasive intervention (e.g., packing cauter) indicated; limiting age-appropriate instrumental activities of daily living (ADL).
3	Severe or medically significant but not immediately life-threatening; hospitalization or prolongation of hospitalization indicated; disabling; limiting self-care ADL.
4	Life-threatening consequences; urgent intervention indicated.
5	Death related to AE

Adverse Event Attribution

Relationship	Attribution	Description
Unrelated to investigational agent/intervention	Unrelated	The AE is clearly NOT related to the intervention
	Unlikely	The AE is doubtfully related to the intervention
Related to investigational agent/intervention	Possible	The AE may be related to the intervention
	Probable	The AE is likely related to the intervention
	Definite	The AE is clearly related to the intervention

Reporting of Adverse Events

AEs may be spontaneously reported by the patient and/or in response to an open question from study personnel or revealed by observation, physical examination, or other diagnostic procedures. Any clinically relevant deterioration in laboratory assessments or other clinical finding is considered an AE. When possible, signs and symptoms indicating a common underlying pathology should be noted as one comprehensive event. For serious AEs, the

investigator must determine both the intensity of the event and the relationship of the event to study drug administration.

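### The phase II toxicity boundary counts only related grade 3-4 events, so a related event recorded only as grade 5 (death) does not move the enrolment-hold trigger

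*Combined protocol and SAP*

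**What the plan says.** Section 9, Safety/Stopping Rules, plans to "monitor and evaluate short term adverse events at each additional 12 patients who have been enrolled in the study". It names the toxicity event in three places, each time with the same closed grade range:

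- The rate sentence: "For the development of grade 3-4 adverse events deemed to be related to MLN9708, the true rate is 5" per cent. It continues that "enrollment will be on hold if more than 10% adverse events are observed".
- The boundary sentence: "The stopping boundaries for graft rejection and development of grade 3-4 adverse events are shown in Table below".
- The column heading of the table: "Stopping boundary for developing grade 3-4 adverse events related to MLN9708". The printed values are at least 3, 4, 6, 6 and 7 at 12, 24, 36, 48 and 51 patients.

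The only other column in that table is immunologic graft rejection. Non-relapse mortality is a secondary objective and has no boundary.

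The Adverse Event Grading table in section 11 runs to grade 5, defined as "Death related to AE". Deaths are handled in the Data Safety Monitoring Plan (section 5) and under Unexpected Adverse Events (section 11). The DSMC receives all grade 4 and 5 events within 5 calendar days and can terminate the study. Neither place adds a grade 5 event to the boundary count or ties an automatic hold to it.

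**The concern.** A boundary of this kind commits the study in advance to pause when toxicity reaches a set count. Here the count stops at grade 4. A related event that first enters the record as a death contributes zero, however many such deaths occur. For a given overall rate of related severe toxicity, the rule therefore becomes less sensitive as more of that toxicity is recorded only as fatal.

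Safety is a primary objective of both phases. The protocol's own account of study C16005 also shows that a related death can occur with this drug: "One death was reported for a patient with RSV pneumonia; the event was deemed by the investigator to be related to treatment with MLN9708".

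**Working it through.** **Reading the passages together.** The counted range is grades 3 to 4 (section 9), and grade 5 is a distinct grade (section 11). Elsewhere the protocol includes grade 5 explicitly: Table 3 uses grade 3 or greater for several toxicities, and the reporting text in section 11 refers to grades 3 to 5. Set against that usage, the wording in section 9 reads as a closed range.

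**Counts at the looks.** Suppose c patients have a related grade 3-4 event and d others have a related event recorded only as grade 5. The count as worded is c. With grade 5 included it is c + d.

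- First look, boundary 3: with c = 2 and d = 1, the count is 2 as worded (no hold) and 2 + 1 = 3 with grade 5 included (hold).
- The same difference of one per death applies at every look.
- With c = 0, any d leaves the count at 0.

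**Operating characteristics of the printed boundary.** The plan states no error rate or power for this boundary, so there is no figure to reproduce. I took the looks n = 12, 24, 36, 48, 51 and boundaries r = 3, 4, 6, 6, 7, with one count per patient and independent patients with event probability p. The marginal probability at a look is P(X ≥ r), X ~ Bin(n, p). For example, at n = 12 and p = 0.05: 1 − 0.54036 − 0.34128 − 0.09879 = 0.0196.

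The cumulative probability comes from carrying forward only the paths still below the boundary:

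- g_k(s) = Σ_x g_{k−1}(s − x) · Bin(x; n_k − n_{k−1}, p), summed over s − x < r_{k−1}
- cumulative hold probability = Σ_k Σ_{s ≥ r_k} g_k(s)

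| True counted rate | Marginal P at the five looks | Cumulative P(hold) |
|---|---|---|
| 5% | 0.020, 0.030, 0.008, 0.032, 0.013 | 0.058 |
| 10% | 0.111, 0.214, 0.145, 0.347, 0.245 | 0.407 |
| 15% | 0.264, 0.495, 0.459, 0.746, 0.660 | 0.784 |
| 20% | 0.442, 0.736, 0.754, 0.938, 0.908 | 0.950 |

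**Effect of leaving out grade 5.** The documents give neither the total related grade 3-5 rate π nor the share f recorded only as grade 5. Both are assumptions here, shown over a range. The counted rate is π(1 − f); for example, 0.10 × (1 − 0.20) = 0.08.

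| π | Grade 5 counted | f = 10% | f = 20% | f = 50% |
|---|---|---|---|---|
| 10% | 0.41 | 0.32 | 0.24 | 0.06 |
| 15% | 0.78 | 0.69 | 0.58 | 0.20 |
| 20% | 0.95 | 0.91 | 0.83 | 0.41 |

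**A separate matter.** Read literally, the text's threshold of more than 10% gives 2, 3, 4, 5 and 6 at the five looks, not the printed 3, 4, 6, 6 and 7. The calculations use the printed table. The point about grade 5 does not depend on which is used.

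**The case against.** **Deaths have their own route, and it is faster.** Every grade 5 event goes to the DSMC within 5 calendar days, whatever its attribution. The boundary is examined only after each further 12 patients, roughly every six months, and crossing it leads to review by the same committee. This stands. A reader might infer that related deaths are unmonitored, and the documents do not support that. What is missing is the pre-specified count and the automatic hold.

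**A fatal course may still be counted.** A reader might infer that the count falls when a grade 4 event ends in death, by joining the boundary to the sentence "Worst toxicity grades per patient will be tabulated for selected adverse events and laboratory measurements". That sentence governs tabulation of selected items, not the boundary. The boundary concerns developing a grade 3-4 event, and a patient who developed one before dying has met that description. So the gap is confined to events recorded only at grade 5. Such records are plausible: section 11 asks that signs of a common underlying pathology be noted as one event where possible, and section 9 does not say how to count such a patient.

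**It may be shorthand.** The same grade range appears in one line of Table 3, under Dose modification and under Duration of therapy, where a deliberate exclusion of fatal toxicity seems unlikely. The authors may have meant grade 3 or higher. No text says so, and a hold rule should not depend on guessing.

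**The related death in C16005 is weak evidence of scale.** A reader might project that one death among 65 patients onto this trial. That study combined MLN9708 with lenalidomide and dexamethasone, in another population and at doses up to 3.95 mg/m². The weekly single-agent studies C16004 (52 patients) and C16007 (14 patients) report no deaths, so 0 of 66. The death shows that the event is possible, not how often to expect it here.

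**Conclusion.** The point holds for the formal enrolment-hold trigger as worded. A related event recorded only as grade 5 adds nothing to the count, and no other boundary covers it. One such death can be the difference between holding and not holding at any look.

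The effect on the probability of a hold depends on rates that the documents do not give. It is modest if few related events are recorded only as deaths (0.41 falls to 0.32 at a 10% total rate with a 10% share) and large if many are (0.41 falls to 0.06 with a 50% share). These figures assume independent patients, one count each and the printed boundary. The finding does not extend to the DSMC's review of individual deaths, which is prompt and can end the study.

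**What to change.** In the section 9 text and in the table heading, define the counted event as patients with at least one adverse event of grade 3 or higher (grades 3-5) related to MLN9708, each patient counted once. State the boundary's operating characteristics for that event. If the printed numbers are kept, the cumulative figures in the first table apply. The sponsor should confirm that the 5% reference rate and the 10% threshold are meant for the redefined event.

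Leave the toxicity tabulation in section 9 unrestricted by grade; limiting it to grades 3-5 would narrow it for no gain. The sponsor should also reconcile the grade 3-4 wording in Table 3, Dose modification and Duration of therapy with the five-grade scale in section 11. Those are clinical rules, and this review takes no position on their content.

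The cost is an edit to the text and heading plus a short statement of operating characteristics. No new data are needed, because grade and attribution are already collected. The boundary becomes slightly easier to reach; at a true counted rate of 5% the chance of a hold is still about 0.06.
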